5.2.1 Screening and informed consent

Eligibility will be confirmed through a series of steps as follows (see inclusion/exclusion criteria for details).

- Medical history and medications.
- The Modified Rankin Scale (MRS) assessed by interview will used to determine functional ability prior to the stroke.
- The Modified mini mental exam (MMSE) [Teng and Chui 1987] is a series of questions (approximately 5 minutes) to assess orientation (e.g. date, place) and ability to follow commands.
- Spasticity will be measured using the Modified Ashworth Spasticity (MAS) Scale [Bohannon and Smith 1987]. The MAS is a 6-point ordinal rating scale for measuring muscle tone, with ratings from 0 (no increase in tone) to 4 (limb rigid in flexion or extension).
- The National Institutes of Health Stroke Scale (NIHSS) is a measure of neurological functioning, with higher scores reflecting greater deficit (maximum 42).
- Chedoke-McMaster Stroke Assessment (CMSA) [Gowland et al. 2003] includes an impairment inventory and an activity inventory. The Impairment inventory includes staging assessments of shoulder pain, postural control, recovery of arm and hand, and recovery of leg and foot. Only arm and hand impairment will be assessed which stages each between 1 and 7 with higher score indicating better motor performance
- The possible presence and severity of depression will be assessed using the Patient Health Questionnaire (PHQ9) [Graves & Bobardier 2008]. The PHQ9 has nine inquiries about the frequency of symptoms associated with depressed mood over the

previous 2 weeks, each scored between 0 (not at all) to 3 (nearly every day). The maximum score is 27 points. Scores that equal 10 or greater are associated with clinical depression. The PHQ9 has been tested and validated in stroke populations with good sensitivity for detecting depression [de Man-van Ginkel, et al. 2012; Janneke, et al. 2012].

Structural MRI

Unless already existing, an MRI will be acquired using a high resolution (1.5T or more) T1 weighted image of the subject's brain on any standard magnetic resonance system. MRI acquisition parameters and instructions are shown in the NBT System User manual.

The subject's structural MRI sliced images will be loaded into the Nexstim NBT system.

5.2.2 Baseline assessment

The following functional tests will be administered by an experienced researcher. Training and certification of the researchers to perform these tests is described in a separate Outcome Assessment Training and Certification Plan

- The *Fugl Meyer (FM)* will measure functional movement. The FM offers impressive test-retest reliability (total=.98-.99; subtests=.87-1.00), and construct validity [Duncan et al. 1983; DiFabio and Badke 1990]. The upper extremity (UE) FM movement scale is a measure of upper limb function, with higher scores reflecting greater function.
- The Action Research Arm Test (ARAT) [Lyle 1981] is used to determine whether fine • motor skill changes occurred in the affected hand and fingers. The ARAT is a 19-item test divided into four categories (grasp, grip, pinch, and gross movement), with each item graded on a 4-point ordinal scale (0=can perform no part of the test; 1=performs test partially; 2=completes test but takes abnormally long time or has great difficulty; 3=performs test normally) for a total possible score of 57. The test is hierarchical in that, if the patient is able to perform the most difficult skill in each category, he/she will be able to perform the other items within the category and, thus, they need not be tested. The ARAT has high intrarater (r = .99) and retest (r = .98) reliability and validity [Lvle] 1981 Van der Lee et al 20011
- *The National Institutes of Health Stroke Scale* (NIHSS) will be repeated at baseline visit.
- *EQ-5D*

The EQ-5D questionnaire is a standardized, well validated instrument for assessing patients' health and quality of life. The questionnaire will be utilized to establish the overall impact of stroke on the patients' quality of life and used to assess possible changes during the trial period.

Diagnostic NBS-TMS session:

• motor mapping of the healthy hemisphere, and determination of motor threshold and the optimal cortical representation area of the muscle of interest

(m.Extensor Digitorum Communis, m.EDC), The NBS protocol is described in detail in appendix A.

5.2.3 Randomization

Randomization will occur using a random number generator programmed to randomize patients to rTMS vs Sham TMS in a 1:1 ratio such that approximately 30 patients will be randomized to treatment and 30 patients randomized to sham. Randomization will be done separately for each participating site so that the 1:1 ratio for treatment arms will be attained at each participating site. In addition, for each site the randomization will be performed in randomly occurring blocks of 3 to 6 patients. Further, patients who have suffered a stroke 3 to 6 months before the trial will be randomized separately from those who have suffered stroke more than 6 months (maximum 12 months) earlier.

The groups differ only as to the rTMS protocol they receive during the study. The groups are : sham rTMS (900 pulses at 1Hz frequency), and active NBS-rTMS (900 pulses at 110% of motor threshold, 1Hz frequency).

5.2.4 Treatment Visits

The visits will last approximately 3 hours and will consist of the following. (For detailed description see appendix B)

- 1. Review with subject any new medical problems, medication changes or symptoms occurring since last visit (e.g. headache, changes in hearing, seizure)
- 2. 20 minutes of pre-functional activities (For detailed description see appendix B)
- 3. 10 minute rest
- 4. 1Hz navigation guided rTMS (For detailed description see appendix A) For patients randomized to receive rTMS, the stimulation will be delivered in a single pulse train 900 pulses given at 110% of motor threshold. The motor threshold will be determined at each visit. The train will be targeted on the motor representation of the m.EDC on the healthy brain hemisphere determined at the baseline visit (NOTE: the rTMS delivery location will thus be the same at each visit).

OR

Sham rTMS

For patients randomized to receive Sham rTMS, the sham stimulation will be delivered in a single 1Hz pulse train of 900 pulses given using a Sham coil. The train will be targeted on the motor representation of the m.EDC on the healthy brain hemisphere determined at the baseline visit (NOTE: the rTMS delivery location will thus be the same at each visit).

- 5. 5-15 minute rest
- 6. 60 minutes of Task-oriented motor rehabilitation of the arm and hand (For detailed description see appendix B).

5.2.5 Outcome Assessments

The visits will take place 5-10 days, 1 month, 3 months and 6 months after the completion of the study treatment visits. The visits will last approximately 3 hours and consist of the following functional tests which will be performed at each and every outcome assessment visit:

- The National Institutes of Health Stroke Scale (NIHSS)
- Fugl Meyer (FM)
 - The Fugl-Meyer test is the primary outcome measure for the trial.
- ARAT
- EQ-5D

5.2.6 Occupational therapy, physiotherapy and home exercise program during the active treatment and follow-up periods of the trial

Occupational therapy:

During the 6 weeks active treatment period of the trial (visits 3-20) the patients are not allowed any other occupational therapy except that provide in the trial. After the active treatment period during the 6 month follow-up period of the trial, patients are allowed occupational therapy. The hours of therapy will be documented. Patients will be queried once every 2 weeks until the final outcome assessment visit at 6 months after end of active trial treatment, either when they visit the study site or they will be called and queried.

Physical therapy:

Patients are allowed participation in physical therapy for the full trial duration including during the active treatment period of the trial (visits 3-20). However, the hours of therapy and time of use of the affected upper extremity in treatment sessions will be documented. Patients will be queried once every 2 weeks until the final outcome assessment visit at 6 months after end of active trial treatment, either when they visit the study site or they will be called and queried.

Home exercise program:

During the 6 weeks active treatment period of the trial (visits 3-20) the patients are not allowed an upper limb home exercise program prescribed by therapists other than the study therapist. The study therapist will provide an upper limb home exercise program for the active treatment period of the trial. The study therapist will also provide an upper limb home exercise program for the post-active treatment period of the trial. However, this home exercise program for the post-active treatment period can be modified by the patient's own therapist based on her/his assessment of the patient's clinical needs. The hours of therapy will be documented. Patients will be queried once every 2 weeks until the final outcome assessment visit at 6 months after end of active trial treatment, either when they visit the study site or they will be called and queried

6.0 ANALYSIS PLAN

The results of functional motor tests at end of rehabilitation (5-10 days post treatment) and at 1, 3 and 6 months after the end of rehabilitation will be compared to the results obtained at baseline to determine the functional recovery if any that has occurred. The results of patients randomized into separate groups will be compared to each other to determine the effect of rTMS.

The primary analysis population will be the intent-to-treat (ITT) population. In addition, a separate analysis will be conducted on the per protocol (PP) population.

Primary outcome measure for the trial is the Upper-extremity Fugl-Meyer score.

The beneficial effect of 1Hz NBS guided rTMS will be established if a statistically significantly greater proportion of patients receiving NBS-rTMS attain clinically important improvement in the primary outcome measure than patients receiving sham-rTMS between baseline and 6 months post-treatment.

The size of the treatment effect will be measured by the odds ratio parameter which is defined as

$$OR = \frac{P_{TRT} / (1 - P_{TRT})}{P_{REF} / (1 - P_{REF})}$$

where P_{TRT} and P_{REF} denote the proportion of subjects with clinically significant change from baseline in Fugl-Meyer score, in the treatment and reference groups respectively.

The null hypothesis is H_0 : OR = 1 and the two-sided alternative hypothesis is H_1 : $OR \neq 1$.

The proportion of responders in each treatment group will be summarized, along with the estimated odds ratio, the 95% confidence interval for OR, and the Wald Chi-square test p-value. The primary analysis will be performed on the ITT, and on the PP population as a sensitivity analysis.

Secondary outcome measures for the trial are ARAT test, , NIHSS, and EQ-5D.

Descriptive statistics will be summarized by treatment and visit. Absolute difference (in points) in improvement will be summarized for both treatment groups between baseline and 5-10 days and 1, 3 and 6 month follow-up visits and the treatment groups compared via a two-way ANOVA.

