The beneficial effect of 1Hz NBS guided rTMS will be established if a statistically signicantly greater proportion of patients receiving NBS-rTMS attain clinically important improvement in the primary outcome measure than patients receiving sham-rTMS between baseline and 6 months post-treatment. Minimal clinically important improvement is defined as an increase of 5 points on the upper extremity Fugl-Meyer score [Page SJ, et al. 2012].

Secondary Assessments	1. Secondary outcome measures for the study are:					
and	Arm-Research Action Test (ARAT)					
Endpoints:	NIH Stroke Scale (NIHSS)					

Quality of life assessment: EQ-5D questionnaire.

The changes on these scales between baseline and 6 months post-treatment will be determined for both therapy groups and the groups compared to each other.

2. Safety endpoint

To assess safety of study device use, all Serious Adverse Events and Unanticipated Adverse Device Events and Device Related Adverse Events will be recorded and compared between therapy groups..

ABBREVIATIONS

APB	Abductor Pollicis Brevis
CRO	Clinical Research Organization

EDC	Extensor Digitorum Communis
EMG	Electromyography
FDA	Food and Drug Administration
fMRI	Functional Magnetic Resonance Imaging
IRB	Institutional Review Board
MEP	Motor Evoked Potential
MRI	Magnetic Resonance Imaging
MT	Motor Threshold
NBS	Navigated Brain Stimulation
NBT	Navigated Brain Therapy
rTMS	Repetitive Transcranial Magnetic Stimulation
SAE	Serious Adverse Events
SD	Standard Deviation
TMS	Transcranial Magnetic Stimulation

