3.2 SECONDARY OBJECTIVES

Secondary outcome measures for the study are:

Absolute change in points on UEFM

Action-Research Arm Test (ARAT)

NIH Stroke Scale (NIHSS)

The changes on these scales between baseline and 6 months post-treatment will be determined for both therapy groups and the groups compared to each other to establish effects of therapy.

Quality of life outcomes:

In addition to the other secondary outcome measures above the patients' quality of life will be assessed using the EQ-5D questionnaire. The change on this scale between baseline and 6 months post-treatment will be determined for both therapy groups and the groups compared to each other to establish effects of therapy on quality of life.

Assessment of safety:

To assess safety of study device use, all Serious Adverse Events, Unanticipated Adverse Device Events and Device Related Adverse Events will be recorded and compared between therapy groups..

4.0 study design

This is a prospective multi-center sham-controlled double-blinded study.

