5.2. VISIT SCHEDULE

The study will be performed over 24 to 29 sessions:

- 1) Visit 1(Screening visit): Baseline = 3-12 months after the stroke. The purpose of this visit is to obtain informed consent for the study (if not previously obtained) and to screen subjects for inclusion and exclusion criteria.
- 2) Visit 2: Baseline assessment. The purpose of this visit is to establish the baseline of injury, motor status and NBS parameters (Localization of cortical motor representation area of the target muscle to which therapeutic rTMS will be subsequently delivered, see appendix A). Subjects will also undergo a structural MRI. The subject will then be randomized to either rTMS or to sham treatment. The baseline visit may if necessary take place on 2 separate days.

- 3) Visits 3-20: During these visits the patient will undergo standardized task-oriented motor rehabilitation of the hand. In addition the patient will receive the rTMS therapy according to the protocol of the group she/he was randomized into during visit 1. The visits will take place during a 6 week period, three visits per week. During each week the visits will take place each on a separate day and a maximum of two visits will take place on consecutive days.
- 4) Visit 21: End of the task-oriented motor rehabilitation. The purpose of the visit is to establish the extent of recovery that has occurred during the rehabilitation. The visit will take place 5-10 days after the last rTMS/rehabilitation session and includes functional motor testing).1-2 visits may be needed to complete assessment.
- 5) Visit 22: 1month (±5 days) after the end of the rehabilitation therapy. The purpose of the visit is to determine whether any changes in motor function have occurred within 1 month of ending therapy. The assessment includes functional motor testing. 1-2 visits may be needed to complete assessment.
- 6) Visit 23: 3 months (±5 days) after end of the rehabilitation therapy. The purpose of this visit is to determine whether any changes in motor function or NBS parameters have occurred within 3 month of ending therapy. The assessment includes functional motor testing. In patients experiencing a new stroke, only the data prior to the event will be used in the analysis. 1-2 visits may be needed to complete assessment.

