6.4 STRATA AND COVARIATES

The primary efficacy analysis will be stratified by length of time after stroke (3-6 months vs. 6-12 months).

Additional covariate analyses will model the primary endpoint (a binary response of UEFM score improvement), absolute changes (in points) in the tests of motor function (UEFM, and ARAT) using hours of occupational therapy outside the trial and overall hours of therapy (occupational, physical, and home exercise) as covariates during treatment phase and over the entire 6 months of follow-up.

All covariate analysis will be performed for both ITT and PP population.

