6.5 SIGNIFICANCE LEVEL

Unless otherwise noted, all statistical analyses will be conducted with a significance level (α) of 0.05 and utilize two-sided testing.

Since the ARAT test has potential to be used for labelling purposes, a Bonferroni adjustment will be employed. A significance level (α) of 0.025 will be used for this secondary analysis only. All other secondary analyses will use $\alpha = 0.05$ as they are not to be used for any labeling purpose.

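### The secondary change scores are compared without the baseline score as a covariate, which probably gives up some precision at almost no saving; an adjusted 6-month contrast should be named as the ARAT test at 0.025

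*Combined protocol and SAP*

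**What the plan says.** Section 6.0 lists ARAT, NIHSS and EQ-5D as secondary outcomes. It takes the improvement in points from baseline to 5-10 days and to "1, 3 and 6 month follow-up visits and the treatment groups compared via a two-way ANOVA". Section 3.2 adds the UEFM point change to the secondary list.

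On timing, the protocol summary says the changes "between baseline and 6 months post-treatment will be determined for both therapy groups and the groups compared to each other", and section 3.2 agrees: "The changes on these scales between baseline and 6 months post-treatment will be determined for both therapy groups". Section 6.5 gives ARAT a Bonferroni-adjusted level because it may be used in labelling: "A significance level (α) of 0.025 will be used for this secondary analysis only".

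On model terms, section 6.4 says "The primary efficacy analysis will be stratified by length of time after stroke (3-6 months vs. 6-12 months" and gives no stratification for the secondary outcomes. Its additional models, which cover UEFM and ARAT point changes, are fitted "using hours of occupational therapy outside the trial and overall hours of therapy (occupational, physical, and home exercise) as covariates". The baseline score is not named as a covariate.

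On the order of events, section 5.2.2 says "The following functional tests will be administered by an experienced researcher" and lists Fugl-Meyer, ARAT, NIHSS and EQ-5D. Section 5.2 places randomisation at the end of that visit: "The subject will then be randomized to either rTMS or to sham treatment". Section 5.2.3 randomises separately by site and by time since stroke.

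Section 6.6.1.2 applies its missing-baseline rules to the secondary endpoints too. The 6-month score is carried back to serve as baseline, or the treatment-arm mean is used when both scores are missing. Section 6.1 refers detailed methods to a separate SAP.

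**The concern.** Subtracting the baseline score is the same as adjusting for it with a slope fixed at 1. ANCOVA estimates the slope from the data. In large samples its variance is never greater than that of the change score, and it is smaller unless the true slope happens to be 1. The baseline scores are measured before randomisation, so they are legitimate covariates, and they are collected anyway.

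The trial has 60 patients, no stated power for any secondary outcome, and one secondary outcome that may reach the label. A change-score comparison without the baseline covariate and the randomisation stratum therefore probably leaves some information unused. Because ARAT has its own significance level, the protocol should also say which contrast that level applies to.

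**Working it through.** **Inputs.** From the documents: 60 patients, 1:1, about 30 per arm (section 5.2.3); four post-baseline visits (section 5.2.5); ARAT level 0.025 and two-sided testing (section 6.5). Assumed, because the documents give no values: the correlation r between baseline and 6-month score, the ratio k of baseline SD to follow-up SD, the correlation between visits, and 80% starting power for ARAT. I also assume that the secondary comparisons use this trial's own patients.

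**1. The plan's own figures.** The ARAT level reproduces: 0.05/2 = 0.025. The 81% power in section 6.1 is for the binary primary endpoint. With 84% against 50% and 30 per arm it is Φ[(0.34 − 1.96 × 0.1214)/0.1132] = Φ(0.90) = 0.816, so it also reproduces, but it does not bear on the secondary scores. There is no secondary power figure to check.

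**2. Precision.** Set the follow-up variance to 1. The change-score variance is k² + 1 − 2rk, and the baseline-adjusted variance is 1 − r². Their ratio is

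(1 − r²)/(k² + 1 − 2rk), which is (1 + r)/2 when k = 1.

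Estimating the slope at N = 60 multiplies this by about 1 + 1/(60 − 4) = 1.018. Ratios after that cost:

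| r | k = 0.8 | k = 1 | k = 1.2 |
|---|---|---|---|
| 0.5 | 0.91 | 0.763 | 0.62 |
| 0.6 | 0.96 | 0.814 | 0.65 |
| 0.7 | 1.00 | 0.865 | 0.68 |
| 0.8 | 1.02 | 0.916 | 0.70 |
| 0.9 | 0.97 | 0.967 | 0.69 |

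Example: r = 0.5, k = 1 gives 0.75 × 1.018 = 0.763. Simulation at N = 60 agrees: 0.765, 0.866 and 0.966 for k = 1 at r = 0.5, 0.7 and 0.9; and 0.91, 0.96, 1.00, 1.02 and 0.97 for k = 0.8. The adjusted slope is r/k, so when k = r it equals 1, nothing is gained and the 2% cost remains.

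**3. What that means for power.** Suppose the change score had 80% power at 0.025, so the standardised effect is 2.241 + 0.842 = 3.083. With k = 1, adjusted power is Φ(3.083/√ratio − 2.241):
- r = 0.5: Φ(1.288) = 90%
- r = 0.7: Φ(1.073) = 86%
- r = 0.9: Φ(0.894) = 81%

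No figure can be given for the stratum, because the documents do not say how strongly time since stroke predicts change.

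**4. If all four visits enter one ANOVA.** Suppose the factors are treatment and visit, and a patient's four scores are treated as independent. The treatment main effect at nominal 0.025 then has true level 2 × P(Z > 2.241/√(1 + 3ρ)), where ρ is the correlation of change scores between visits:
- ρ = 0.3: 10.4%
- ρ = 0.5: 15.6%
- ρ = 0.7: 20.3%
- ρ = 0.9: 24.4%

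By contrast, simulated analyses of the 6-month change alone (t-test, treatment by stratum, or ANCOVA) reject in 2.4% to 2.6% of null trials.

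**5. Missing baseline.** Carrying the 6-month score back sets that patient's change to zero. If 2 of 30 baselines per arm were missing (an assumption), the change-score effect would shrink to 28/30 = 0.93 of its true size. With a mean gain of 0.5 SD, the ANCOVA estimate would be 0.94 to 0.97 of the true effect. Filling with the overall baseline mean leaves it at 1.00 in simulation.

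**The case against.** **The separate SAP may already contain the model.** Section 6.1 refers detailed methods to it, and a protocol may name a test and leave the terms to its SAP. This stands: the gap is in the supplied text, and the first step is to check that document.

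**The gain may be small.** Section 5.2.2 gives ARAT reliabilities of .98 and .99. These are not correlations between baseline and 6 months, but they do not rule out r near 0.9, where the equal-SD gain is about 3% of variance. With a baseline SD below the follow-up SD it can be nil or slightly negative. This also stands, and it is why the result is given as a range. In the other direction, ARAT stops at 57, so patients who start near the top can gain little, which is a reason to doubt a slope of exactly 1.

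**A reader might infer that the ARAT test will exceed its 0.025 level.** The documents do not support that. The 10% to 24% figures need visits pooled as independent rows, which no section states. The protocol summary and section 3.2 set baseline to 6 months as the comparison, and treatment by stratum on the 6-month change is also a two-way ANOVA that holds its level. What remains is that section 6.5 does not tie 0.025 to the 6-month contrast in words.

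**Missing baselines should be rare,** since assessment precedes randomisation. That is fair. The rule matters here only because it would put post-randomisation or arm information into the new covariate.

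**Conclusion.** The point holds as a matter of precision. The supplied text compares secondary change scores without the baseline covariate and states the randomisation stratum only for the primary analysis. With assumed correlations of 0.5 to 0.9 and equal SDs, adjustment leaves about 77% to 97% of the variance at 60 patients. With a baseline SD 1.2 times the follow-up SD it leaves 62% to 70%, and at 0.8 times 91% to 102%.

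It would be wrong to read this as bias, because the randomised change-score comparison is unbiased. It would also be wrong to read it as a demonstrated type I error failure, because that depends on one of several possible readings. The primary analysis is not affected. The change is worth making because the data are already collected, the likely gain exceeds the cost in most of the settings examined, and ARAT may be used in labelling. Confidence is moderate, because all correlations and SDs are assumptions and the separate SAP was not available.

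**What to change.** In section 6.0, and in the separate SAP if it does not already say so:

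- Analyse the 6-month change in ARAT, NIHSS, EQ-5D and UEFM points by ANCOVA on treatment, baseline score and time-since-stroke stratum.
- State whether site, also used in randomisation, is in the model.
- Name the 6-month treatment contrast as the ARAT test at 0.025, in line with the protocol summary and section 3.2. Label the other visits supportive.
- If all visits are modelled together, account for within-patient correlation, for example by a mixed model with the same terms plus visit and treatment by visit. Say that this replaces LOCF for these endpoints.
- In section 6.6.1.2, for these endpoints, do not fill a missing baseline from the 6-month score or the treatment-arm mean. Use pre-randomisation information only, such as the overall baseline mean, with the same value in the change and in the covariate.

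**Cost.** Wording, minor programming and no new data. Baseline and stratum use two degrees of freedom (60 − 4 = 56 left), and slope estimation costs about 2% of variance. Site, with five centres, would use four more. An unstructured covariance over four visits needs 4 × 5/2 = 10 parameters, which is heavy at this size, so the single-visit ANCOVA is the simpler choice.
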